## **2.2 Median sternotomy**

Median sternotomy remains the most common incision used for cardiac surgical procedures as it offers straightforward access to all cardiac chambers and to the origins and proximal portions of the great vessels. This incision can also be used to repair aortic arch lesions and descending thoracic aortic lesions.

A straight vertical midline skin incision is generally made in patients undergoing a median sternotomy. This incision commences several centimeters below the suprasternal notch and extends to the tip of the xiphoid. The exact midline over the sternum then is scored with the cautery. A retractor elevates the upper angle of the vertical skin incision, placing the underlying tissues on tension. The soft tissue is separated from the superior

surface of the manubrium, and a right-angled clamp is passed over the denuded manubrium into the space behind, hugging the bone. The clamp is spread to create a space for the tip of the sternal saw. The suprasternal ligament is cut with the cautery.

The blade of an electric or air-driven saw is held snugly against the posterior surface of the manubrium with the cutting edge against the superior manubrial surface. After activating the saw, the surgeon cuts the manubrium and sternum, staying precisely in the midline. The tip of the saw is kept elevated so that the toe of the saw hugs the back of the sternum. During sawing, the anesthesiologist should cease ventilating the patient and exert no pressure on the lungs, so that the soft tissue and pleura will fall away from the sternum. Drifting away from the midline with the saw must be avoided because the sternum will not spread evenly, and its later closure will be more difficult.

Alternatively, the sternum can be divided from the bottom up. The xiphoid process is mobilized or excised, and the tip of the blade is introduced beneath it. In neonates and infants, the xiphoid process may be excised, the costal margin on either side elevated by sharp retractors, and sharp, well-aligned scissors used to cut the sternum in the midline, from below upward.

When the incision is properly made, the pleural spaces are infrequently entered. A thin layer of bone wax is spread over the bone marrow, primarily where the bleeding is active. When the sternum is fragile, as in older patients, it is better to avoid wax altogether. Bleeding points in the cut edge of the anterior and posterior sternal periosteum are cauterized, but excessive cauterization should be avoided. A retractor is inserted and opened just enough to permit dissection. After a few minutes, it is opened further. It should be opened no more than is necessary for the procedure, because excessive retraction, particularly of the upper half of the sternum, may cause rib fractures, dislocation of costochondral junctions, injury to the brachial plexus, and damage to the stellate ganglion.

Dissection continues by incising the fascia that envelops the thymus gland. The right and left lobes of the thymus are separated up to the level of the brachiocephalic vein. In infants

and children, and occasionally in adults, the thymus may be sub-totally resected, leaving only the cervical portion cephalad to the brachiocephalic vein, to avoid expanding hematomas that may cause postoperative bleeding. The pericardium is then opened longitudinally in the midline, from the diaphragm below to the brachiocephalic vein above. Where this incision meets the diaphragm, care must be taken not to incise the parietal peritoneum. If entry is made into the peritoneal cavity, the opening is sutured to avoid sequestration of blood and fluid in it. The pericardium is cut at right angles to the longitudinal incision at its diaphragmatic end, farther on the left than on the right, after pushing back the pleura to avoid entering the pleural spaces. Pericardial stay sutures are then placed.

### **2.3 Complications following median sternotomy**

Sternal wound complications following median sternotomy remain a challenge in cardiac surgery with a severe burden for the patient and high costs for health care providers. According to previous studies, superficial problems occurred in 1.1–6.7% whereas the incidence of deep sternal wound complications ranged from 0.1 to 3.7%.

A change in the spectrum of cardiac surgery has been observed in recent years. Patients are older, suffer more frequently from diabetes mellitus and have a higher average body mass index (BMI). There is a decreasing number of surgical bypass grafts accompanied by a trend towards more valve operations and complex procedures. In addition, the frequency of emergency procedures is rising.

### **2.4 Surgical site infection**

Over 234 million surgeries are performed around the world every year, yet despite the remarkable advances in surgical technologies and anaesthetic techniques, surgical site infections (SSIs) remain a major cause of patient morbidity and mortality. SSIs are potential complications associated with any surgical procedure; however, they are the most preventable hospital acquired infection (HAI). It is estimated that SSI will occur in up to 9.5% of inpatient surgical procedures. SSI is defined as any infection occurring within 30 days after surgery or within 12 months of surgical implantation of a prosthesis or foreign body.

Millions of surgical procedures are conducted around the world each year. Most procedures result in surgical wounds that heal by primary intention, where wound edges are re-approximated using sutures, staples, clips or glue. Some surgical wounds are left open to heal (where closure is not appropriate because of infection, physical impossibility of approximating wound edges or because of the need to allow drainage) and some wounds break down following closure; these open wounds heal from the 'bottom-up' (known as 'healing by secondary intention').

Surgical wounds are at risk from microbial contamination and thus possible infection. Contamination may originate from the patient, for example when microbes on the skin enter a wound, or from the surrounding environment, for example from operating staff, the theatre, or wider hospital and home environments. SSI was identified as the leading cause of hospital-acquired infection in a systematic review of studies in low-and middle-income countries.

SSI is a serious global issue that can lead to significant morbidity, need for re-intervention and treatment (including antibiotic use), delayed wound healing, and in very serious infections, the possibility of death. SSIs also increase consumption of healthcare resources. Recent figures from the UK suggest that SSIs lead to a median increased hospital stay of 10 days (95% confidence interval (CI) 7 to 13 days) with an associated median additional cost attributed to SSI of GBP 5239 (95% CI GBP 4622 to 6719). The UK National Institute for Health and Care Excellence (NICE) identified that an SSI increased the costs of surgery by two to five times. In the USA, Lissovoy et al estimated that the extended length of stay and increased treatment costs associated with SSIs over a one-year period led to approximately 1 million additional inpatient-days, costing an additional USD 1.6 billion.

### **Definition of SSI**

Although there is no single agreed diagnostic tool or protocol to confirm the presence of an SSI, Bruce et al identified 41 different definitions for SSI and 13 grading scales, the Centers for Disease Control and Prevention (CDC) definition is commonly used.

A **superficial SSI** is defined as: an infection occurring within 30 days after the operation and only involving the skin and subcutaneous tissue of the incision that is associated with at least one of the following:

- Purulent drainage, with or without laboratory confirmation, from the surgical site;
- Organisms isolated from an aseptically-obtained culture of fluid or tissue from the surgical site;
- At least one of the following signs or symptoms of infection: pain or tenderness, localised swelling, redness or heat, *and* superficial incision is deliberately opened by the surgeon and is culture-positive or not cultured. A culture-negative finding does not meet this criterion;
- Diagnosis of SSI by the surgeon or attending physician.

A **deep incisional SSI** is defined as: infection that occurs within 30 days after the operative procedure if no implant is left in place, or within one year if an implant is left in place, and the infection appears to be related to the operative procedure *and* involves deep soft tissues (e.g. fibrous connective tissues and muscle layers) of the incision associated with one of the following:

- purulent drainage from the deep incision, but not from the organ/space component of the surgical site;
- a deep incision spontaneously dehisces (opens up) or is deliberately opened by the surgeon and is culture-positive or not cultured when the patient has at least one of the following symptoms: fever or localised pain or tenderness;
- an abscess, or other evidence of infection involving the deep incision is found on direct examination, during re-operation, or by histopathologic or radiologic examination;
- diagnosis of a deep incisional SSI by a surgeon or attending physician.

## **Interventions**

Many interventions are used with the aim of reducing the risk of SSI in people undergoing surgery. These interventions can be delivered at three stages: preoperatively, intraoperatively and postoperatively

- Preoperative phase: the time period between the decision for the need for surgery and when everything is ready for the operation to start, that is, the patient is on the operating table.
- Intraoperative phase: the time period from when the patient is on the operating table to when the operation has finished and the wound is closed (if relevant). Any activity taking place after induction of anaesthesia to be in this phase because this starts in the operating theatre itself.
- Postoperative phase: as the time period from the end of the intraoperative phase to resolution of surgical procedure. Whilst dressings, wound drains and negative pressure wound therapy are often placed over wounds at the end of surgery, their use is predominantly outside of theatre, so they are considered in the postoperative phase.

### **2.5 Risk factors for sternal wound infections**

The risk factors for sternal wound infection is multifactorial. Any factors that contributes to poor wound or bone healing (e.g. malnutrition, osteopenia) or increases the risk for surgical site infection (e.g. diabetes mellitus, immunosuppression) may influence the manifestation of sternal wound infection, especially if two or more factors are present. There are several retrospective and prospective studies that have identified other factors relating to sternal wound infection. It is included obesity, diabetes mellitus, hypertension, chronic obstructive lung disease (COPD), smoking, steroid therapy, immunosuppression, advanced age, congestive heart failures, and respiratory failures.

There are also technical factors that play a role in the risk of sternal wound infection or even sternal dehiscence. It may include prolonged operative time, the need for chest compression, postoperative bleeding, intraoperative complication, transfusion, reoperation, asymmetric sternotomy incision that is difficult to realign, bone ischemia due to excessive use of electrocautery or possibly internal thoracic artery harvesting

(especially if bilateral), or even the excessive use of bone wax around the sternal edges intraoperatively. 

### **Bone Wax**

Bone wax was first introduced in medicine in 1886. It is a sterile stick and is used as a topical haemostatic material composed of a softening agent such as Vaseline and beeswax. When it is applied on the surface of the bones, it remains indeterminately and may cause various adverse effects. 

At first the primary reason for using bone wax is to maintain haemostasis. However, it has no biological or chemical hemostatic effect. One study stated that the hemostatic effect of bone wax is associated with the physical blocking of the holes in the bone and stopping the blood flow from damaged vessels into the bone. However, the literature data do not support a reduction of blood or blood product consumption as a result of a presumably decreased perioperative blood loss when using bone wax. 

Additionally, bone wax is known to inhibit bone healing and osteogenesis. It inhibits the osteoblastic activity, prevent bone healing and may lead to creation of a pseudo-arthritis. A sternal wound is different than other bone wound, it is associated with the exertion of dynamics of a chest wall mobility especially in the work of breathing. Thus, the osteogenesis and the wound healing is very important. It is reported that chronic inflammatory reactions with the presence of residual bone wax exist up to 10 years after the operation. 

Bone wax is not an absorbable or metabolized material. It may induce a foreign body reaction which characterized by giant cells, plasma cells, fibrous tissue, and a lack of bone formation, that may trigger an allergic reaction or granuloma formation.  In an anatomic-pathology study of 18 cadavers by Sudmann et al, it was reported that bone wax induces chronic inflammation and granuloma formation in the sternum postoperatively. 

Moreover, bone wax has shown to be related with pulmonary embolic events. In an experimental study, in which, there were radioactively labelled bone wax applied at the sternal wound. It was found that bone wax accumulated in significant quantities in the

lung. This shows that bone wax may embolize and may give rise to secondary pulmonary complications.

## **2.6 Deep sternal wound infection**

[figure not shown]
Deep sternal wound infection (DSWI) is a serious postoperative complication of cardiac surgery. According to the literature, the incidence of DSWI after cardiac surgery has been variously reported as between 0.8 and 5.0%. This postoperative complication is a serious one, being responsible for a mortality rate varies between 19% and 29% in different series of adult cardiac surgical patients. Based on JACVSD registered data from 2004 to 2009, the overall incidence of DSWI after cardiac surgery was 1.8%, as for each operative procedure, the incidence of postoperative DSWI was 1.8% in isolated CABG group, 1.3% in valve group, 2.8% in valve with CABG group, 1.9% in thoracic aorta group and 3.4% in thoracic aorta with CABG group. When operative procedure concomitant with CABG was done, the incidence of postoperative DSWI showed 1.5% of elevation compared with isolated original valve and thoracic aortic procedure. Internal thoracic artery use, prolonged operative time and longer cardiopulmonary bypass time are possible mechanisms to explain these increased rates of DSWI.

## **2.7 Sternal dehiscence**

[figure not shown]
Sternal Dehiscence is a serious complication of cardiac surgery which is often a predecessor to mediastinitis, in fact it is often accompanied with mediastinitis. The incidence of sternal dehiscence after median sternotomy is varied between 0.5% to 8.4%. Sternal dehiscence is defined as the separation of the edges of the sternum from one to another and can occur in the absence of soft tissue dehiscence. This condition can be caused by wire fracture, loosening, or “puling through” the sternal edges.

Patients may complain of a painful chest motion and “clicking”. The diagnosis is made upon physical examination by placing each hand on either side of the sternum and having the patient cough, which will cause a click or “rocking” of the sternum^64. Sternal dehiscence is a surgical emergency as the complication may include an increased risk of ventricular rupture due to sharp wires or bone fragments rubbing against the heart. When sternal dehiscence occurs in the early postoperative period, the patient is taken to the operating room for exploration.

## Theoretical Framework

## Conceptual Framework

## **Chapter 3**

### **Methods**

#### **3.1 Design**

This study will adopt a single blind randomized control trial design for 3 months.

#### **3.2 Time and location**

This study will be conducted for 3 months, starting from December 2019 – February 2020. It will be held at the National Cardiovascular Centre Harapan Kita, Jakarta, Indonesia.

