### Method

This study will adopt a single blind, single center, randomized control trial design for 3 months.

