### Introduction

#### 1.1 Background

Nowadays, a high volume of cardiac surgery has been performed at National Cardiovascular Centre Harapan Kita, Jakarta, Indonesia. In 2017 there were 1721 cardiac surgery conducted in the adult cardiac surgery division. Of those, 801 were coronary artery bypass graft surgeries, 598 were heart valve repair and replacement surgeries, 93 were vascular surgeries, 116 were congenital cardiac surgeries, 8 surgeries in intracardiac tumour, and 105 other cardiac surgeries.

In cardiac surgeries, the current approach established is through median sternotomy. The sternum consists of a low vascularized tissue and it may be damaged especially when internal thoracic arteries are used for coronary artery bypass grafting. Thus, the postoperative complication related to sternal healing are common. The sternotomy wound may be complicated with partial or complete sternal dehiscence and sternal wound infection, osteomyelitis or even mediastinitis. Surgical site infection (SSI) involving the sternum is a distressing complication in cardiac surgery. The incidence of postoperative superficial and deep SSI in cardiac surgery varies from 1.3 to 12.8%.

Subsequent to median sternotomy, bone wax has been applied for decades as a mechanical barrier to maintain the haemostasis on the surface edges of the sternum. Bone wax is a nonabsorbable substance and it is believed that bone wax may cause inflammation as it is produced foreign body reaction and mechanically inhibit osteoblastic activity, which may eventually lead to increased risk of postoperative sternal dehiscence. Apparently, the use of bone wax has no clear recommendation in any guidelines and there are still controversies regarding the efficacy and safety of the application of bone wax.

To overcome the problem that may be related to the use of bone wax. Different innovative approaches are evaluated, including, a non-woven material to protect the sternum during operation. Sternum Guard™ is a single use, sterile surgical drape, for sternal protection,

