#### **3.4 Inclusion and exclusion criteria**

Inclusion Criteria:

1. Patients ages > 18 years old
2. Patients who are scheduled electively for cardiac surgery
3. Cardiac surgery with the usage of cardiopulmonary bypass machine
4. Patients who are agreed to participate in this study

Exclusion Criteria:

1. Patients who are scheduled for surgery in emergency or urgent manner
2. Patients with the history of uncontrolled hypertension and uncontrolled diabetes mellitus.
3. Patients with the history of past cardiac surgery

Drop – out Criteria:

1. Patients who are pronounced death on operation table
2. Patients who are pronounced death within hospitalization
3. Patients who are lost to follow up (Day 30 post-operative)
4. Patients who are not committed for the whole stage of the research

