### **3.6 Data extraction**

Every participant included in this study will be scheduled for any cardiac surgery electively. Every participant will undergo the surgery with cardiopulmonary bypass. All of the surgery will be conducted in a similar manner, however, if there is any complication intraoperatively, every action will be taken according to the situation and will be recorded. Before incision the Sternum Guard™ and sterile drapes for the bone wax group will be weighed. After median sternotomy, the surgeons will be given Bone Wax or Sternum Guard™ to be applied to the sternum. The decisions will be made based on the block randomisation technique and will be informed beforehand to the nurse scrub and the surgeon. In the Bone Wax group, cauterization will be used according to the sternum's condition and surgeon's decision before applying the sterile draping and after removing it if needed. In the Sternum Guard™ group, cauterization will also be applied before inserting it to the sternum and after removing the Sternum Guard™ if needed.

Subsequent to median sternotomy, sternal bleeding will be assessed. In the Sternum Guard™ group, immediately before cauterization and in Bone Wax group right before applying the bone wax.

Once the surgery is done, the Sternum Guard™ and the sterile drapes will be weighed again. Sternal trauma will be evaluated at the end of surgery (visible trauma or no visible trauma). In the Sternum Guard™ group, within 5 minutes of Sternum Guard and sternal retractors removal and on the Bone Wax group within 5 minutes of removal of the sterile drapes and sternal retractors. Another sternal bleeding assessment will be done on both groups. In the Sternum Guard™ group it will be assessed immediately after removing the Sternum Guard, before the cauterization, while on the Bone Wax group, before applying any bone wax and cauterization. The sternotomy wound will be evaluated and documented at Day 0, at the end of hospital stay, Day 14 post - operative, and Day 30 post-operative. After the surgery, the surgeons will be given questionnaire regarding the use of Sternum Guard™ as opposed to Bone Wax.

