### 3.7 Sample size estimation

The sample size in this study is estimated by using the formula for hypothesis tests for two population proportions (two-sided test)

$$n = \frac{\left\{ Z_{1-\alpha/2} \sqrt{2\bar{P}(1-\bar{P})} + Z_{1-\beta} \sqrt{P_1(1-P_1) + P_2(1-P_2)} \right\}^2}{(P_1 - P_2)^2}$$

details:

$\alpha$  : 5

$1-\beta$  : 90

$P_1$  : 0.15

$P_2$  : 0.05

$n$  : 376

From the equation above, it is estimated for the sample size of the study to be 376 samples, with estimated drop out proportion of 10%, it is deduced the sample size of 414 samples.

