#### B. Treatment Group with Sternum Guard™:

Group of patients who undergo cardiac surgery with the use of cardiopulmonary bypass and use Sternum Guard™ to protect the sternum after median sternotomy.

Table 1 - Table of Operational Definition

	Variable	Definition	Type of Data	Code
1	Age	The age of participant when undergo the cardiac surgery, it defines with calculated birth year taken from the medical record	Numerik	
2	Gender	Gender which is included in this study are based one the	Categorical	1 = Male 2 = Female

		data recorded in the medical record.		
3	Comorbid	Data extracted from anamnesis and the medical record, with blood pressure $\geq 140/90$ mmHg and diabetes mellitus (Fasting Blood Glucose $>126$ mg/dL or 2 hr post prandial blood glucose or one time blood glucose $>200$ mg/dL)	Categorical	1 = Yes 2 = No
6	Cardiac Surgery	Any cardiac surgery that are conducted in adult cardiac surgery division which are using cardiopulmonary bypass	Categorical	1 = CABG 2 = Valve 3 = CABG + Valve 4 = Vascular
7	Surgical Site Infection	Surgical site infection is divided by 2 categories (Superficial: infection occurs just in the area where the incision is made; Deep: occurs beneath the incision area in muscle and the tissues surrounding the muscle). It is evaluated at day 0, at the end of hospital stay, day 14 post – operative and day 30 post-operative	Categorical	1 = Deep 2 = Superficial
8	Sternal Dehiscence	Occurs when there is an evidence of sternum separation. Often	Categorical	1 = Yes 2 = No

[figure not shown]
		accompanies with mediastinitis.		
9	Haemostasis Effect	The data obtained by quantity of blood lost from the sternal edges in Sternum Guard TM and Bone Wax group. The Sternum Guard TM and sterile drapes will be weighed digitally before and after surgery to estimate the blood lost.	Numeric	
10	Satisfaction Rate	The result obtained by the questionnaire in both groups.  Overall satisfaction rate  Maintenance of a dry surgical field during intervention (both groups)  Haemostatic effect  Ease of insertion (Sternum Guard TM group)  Ease of removal (Sternum Guard TM group)	Categorical	1 = Satisfied 2 = fairly satisfied 3 = fairly dissatisfied 4 = dissatisfied
12	Experience satisfaction rate	The result obtained by the questionnaire for the Sternum Guard TM group.	Categorical	1 = worse 2 = similar 3 = better

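### The stated 3 months and the target of 414 do not fit together: at the only volume given, 414 is 96% of all the division's operations before any eligibility criterion is applied

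*Combined protocol and SAP*

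**What the plan says.** The length is given three times. The Method paragraph of the Abstract says "This study will adopt a single blind, single center, randomized control trial design for 3 months", section 3.1 says "This study will adopt a single blind randomized control trial design for 3 months", and section 3.2 adds the dates: "This study will be conducted for 3 months, starting from December 2019", ending February 2020. Section 3.3 recruits from one adult cardiac surgery division.

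Section 3.7 arrives at 376 patients and adds 10% for drop-out: "it is deduced the sample size of 414 samples".

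The only volume is in section 1.1: "In 2017 there were 1721 cardiac surgery conducted in the adult cardiac surgery division".

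The type of operation is broad. Section 3.6 says "Every participant included in this study will be scheduled for any cardiac surgery electively", and Table 1 in section 3.11 defines the surgery as "Any cardiac surgery that are conducted in adult cardiac surgery division which are using cardiopulmonary bypass". Section 3.4 then narrows the pool. Patients must be over 18, elective, on bypass and consenting. The exclusions begin with "Patients who are scheduled for surgery in emergency or urgent manner" and also cover uncontrolled hypertension and diabetes, and previous cardiac surgery.

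In the Appendix cost tables, Table 6 lists 207 Sternum Guard devices. Table 5 lists 30 staff hours a week and 360 hours in total.

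The readable text gives no accrual rate, eligible fraction or consent rate. It does not say whether the end date or the target closes recruitment.

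**The concern.** A sample size delivers its power only if it is reached. Here the period and the target are both stated as fixed, and the centre's own figure leaves almost no room between them. If the dates govern, the trial would probably enrol fewer than 414 and could still be reported as having the 90% power in 3.7. A non-significant result on infection or dehiscence would then look more informative than it is. If the target governs, size and power hold, but the stated period and the staff budget are too short. No estimate is biased either way. What is at stake is whether the stated power describes the trial that is run.

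**Working it through.** **1. The plan's own size.** Inputs from 3.7: two-sided 5%, power 90%, P1 = 0.15, P2 = 0.05, so the mean proportion is 0.10.

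- First term: 1.960 × √(2 × 0.10 × 0.90) = 0.8315
- Second term: 1.2816 × √(0.15 × 0.85 + 0.05 × 0.95) = 0.5361
- n = (0.8315 + 0.5361)² / 0.10² = 187.0, rounded up to 188 per arm, or 376 in total
- Drop-out: 376 × 1.10 = 413.6, or 414

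Both stated figures reproduce. Solving the same formula for power with n evaluable per arm:

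power = Φ[(0.10 × √n − 0.8315) / 0.4183]

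With n = 188 this gives 0.901.

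**2. Operations available.**

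- 3 months: 1721 / 4 = 430.25
- Share needed: 414 / 430.25 = 96.2%
- Margin for all exclusions and refusals together: 430.25 − 414 = about 16 operations

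**3. The budget.**

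- Devices: 414 / 2 = 207, as in Table 6, so supply is planned to the target
- Staff: 360 / 30 = 12 weeks, or 84 days, so staffing is planned to the period
- Operations in 84 days at the 2017 rate: 1721 / 365 × 84 = about 396, fewer than 414 even if every patient enrolled

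**4. If recruitment stops at the date, or instead runs to 414.** Let f be the share of all operations that is enrolled. The document gives no value, so 60–90% is an assumption. Equal arms are assumed (consistent with 207 devices), with 10% lost, so evaluable per arm = 430.25 × f × 0.9 / 2. Months to reach 414 = 414 / (1721 / 12 × f). Annual volume needed to reach 414 in 3 months = 414 × 4 / f.

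| f | Enrolled in 3 months | Power | Months to reach 414 | Annual volume needed |
|---|---|---|---|---|
| 100% (limit) | 430 | 0.910 | 2.9 | 1656 |
| 90% | 387 | 0.879 | 3.2 | 1840 |
| 80% | 344 | 0.838 | 3.6 | 2070 |
| 70% | 301 | 0.787 | 4.1 | 2366 |
| 60% | 258 | 0.722 | 4.8 | 2760 |

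Against 1721 in 2017, the volumes in the 90% and 60% rows are 7% and 60% higher.

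**The case against.** The strongest reply is that this is a forecast about accrual and not a fault in the sample size. That stands as far as it goes. A reader might infer that the 414 or the 90% in 3.7 is miscalculated. It is not, and nothing in the document says recruitment stops at the date whatever the count.

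The volume is also two to three years older than the study. The 430 is a ceiling only at the 2017 rate. With 10% growth the target would be 87% of all surgery, and with 20% growth 80%. That is still demanding, but the 16-operation margin is not a fact about 2019–20.

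Three stronger readings are tempting and should not be adopted.

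- **That 414 is impossible because day-30 visits must also finish by February 2020.** Follow-up inside the dates would worsen the shortfall. But Table 4 has a column for March 2020, its marks cannot be read, and the text does not say when follow-up closes.
- **That the comorbidity exclusion removes a large share.** Section 3.4 joins uncontrolled hypertension and uncontrolled diabetes with a bare conjunction, so it may mean either or both. Table 1 and the dummy tables also expect enrolled patients with hypertension and diabetes. The number removed cannot be determined.
- **That only the surgery types coded in Table 1 count.** The definition beside those codes covers any bypass surgery in the division.

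The reply does not remove the mismatch itself. It rests on the plan's own figures, and no growth in volume is claimed to close it.

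**Conclusion.** The concern holds as a conflict between the stated period and the stated size. At the only volume given, 414 patients in 3 months is 96% of all operations before any criterion in 3.4 applies, and the 12 weeks of budgeted staff time cover fewer operations than the target. Losing under 4% of operations to the urgency, bypass, previous-surgery, comorbidity and consent criteria combined is not credible without a clearly higher volume.

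The effect on power is conditional. If recruitment runs to 414, power is as stated and only the period is wrong. If it stops at the date, power for 15% against 5% is about 72–88%. That range rests on the 2017 volume, 3 full months of recruitment, 10% drop-out, equal arms and the assumed 60–90% enrolled share. The 96% depends on the volume alone. This should be corrected before the plan is relied on, but it is not an error in 3.7 and does not bias any comparison.

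**What to change.** Decide which quantity governs, and say so.

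- **If the target governs:** in the Abstract, 3.1 and 3.2, replace the fixed 3 months with a statement that recruitment ends when 414 patients are randomised and data collection ends 30 days after the last operation. Add a projected length. At the 2017 volume this is about 3.2–4.8 months of recruitment at 90–60% enrolled, better replaced by a projection from the centre's recent count. No patients are added beyond those planned. The cost is a longer study (about 0.2–1.8 months more recruitment, plus 30 days if day-30 visits are not already counted) and staff time beyond the 12 weeks in Table 5.
- **If the dates are fixed:** in 3.7, replace 414 and 90% with the number expected from the centre's recent count of eligible elective bypass cases, and the power that number gives by the same formula. This costs only restated figures, at the price of openly lower power.
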